7.4. Baseline pregnancy test and contraception

Females of childbearing potential will have a urine pregnancy test (hCG) performed at the screening visit. This will not be required for menopausal women who have been without menstrual period for at least 1 year. A negative pregnancy test is required for females of childbearing potential to be included in the study. Fertile women must use highly effective birth control methods during the entire period of the trial, unless their partner is vasectomized or in the case of sexual abstinence. Highly effective methods include hormonal contraception (birth control pills, intravaginal or transdermal patch or injection), intrauterine device (IUD), and intrauterine hormone-releasing system (IUS). Fertile male participants should use condom during the entire period of the trial.

AUTHOR: [name], The Parker Institute, Copenhagen University Hospital

DATE: 2020-12-14

Protocol number P142; Version: 4; EudraCT: 2019-002394-59, Regional Ethical Committee Journal Number H-20047715. ClinicalTrials.gov Identifier:

In the event of subjects becoming pregnant during the trial, they are instructed to notify the investigator immediately. If a partner of a male participant becomes pregnant, the investigator should be notified immediately.

8.INTERVENTIONS AND OBSERVATION

8.1 Examinations and testing

Participants will be subjected to a variety of examinations, questionnaires and testing during screening, enrolment and allocation, medical intervention visits, end of treatment and end of trial visits, (see table 1; visit schedule). Blood testing with standard biochemistry (C-reactive protein, Alanine Aminotransferase, Alkaline phosphatases, bilirubin, calcium, creatinine, potassium, sodium and hematology (hemoglobin, leucocytes, differential cell count, erythrocyte, erythrocyte volume fraction, erythrocyte middle volume, erythrocyte middle cell hemoglobin concentration, thrombocytes, reticulocytes), will be performed at screening visit, week 12 and week 24. Blood samples are drawn in order to monitor participants' liver and kidney function, inflammation markers and overall hematology, for safety. The sample will contain 10 ml of blood and will be destroyed after analysis. Urine samples for pregnancy tests and screening for Cannabinoid (THC) and opioid concentration in the urine, will be performed for safety and to ensure that participants are complying with the study protocol. The sample will contain 100 ml of urine and will be destroyed after analysis. Vital signs including blood pressure, systolic and diastolic and resting pulse (sitting down) will be monitored at all visits. ECG (12-lead) will be assessed at the screening visit. Participants will also undergo screening for potential psychiatric side effects including suicide risk, at the screening visit.

8.2. Pre-randomization run-in-period

After the screening visit, a pre-randomization run-in-period of up to 4 weeks starts (week -4 to 0), to ensure that potential participants fulfill all the inclusion criteria and have none of the exclusion criteria. Participants may continue with other prior medications for their pain if they wish (except for opioids).

8.3. Drug intervention period

Eligible participants will be randomly assigned 1:1 to receive cannabidiol 50 mg or an identically appearing placebo. All participants (independent of group) will be titrated up to 50 mg following a dose escalation scheme: Initial dosage of 10 mg daily (week 0), escalated every third day by 10 mg up to week 2. Subsequently participants will stay on 50 mg dosage until the week 24 end of treatment visit. Visits will be conducted weekly during the up-titration period (week 0, 1 and 2), and subsequent visits will take place at week 4, 8, 12, 16, 20 and 24, (see figure 1, Trial design and table 1. Visit schedule). Visits 1, 8 and 16 will be

AUTHOR: [name], The Parker Institute, Copenhagen University Hospital

DATE: 2020-12-14

Protocol number P142; Version: 4; EudraCT: 2019-002394-59, Regional Ethical Committee Journal Number H-20047715. ClinicalTrials.gov

Identifier:

performed as a telephone visit. Medical monitoring of vital signs and clinical and laboratory evidence of potential adverse events will be conducted throughout the study.

8.4. Study drug use, content and handling

Cannabidiol will be administrated to the participants orally in tablet form. Participants will start with 10 mg daily and the dose will be escalated every third day until the maximum dosage of 50 mg is reached (after two weeks). Dose escalation will be based on safety and tolerability, and if dose escalation is not feasible, then delayed increments are allowed. Subjects will be maintained at the highest tolerated dose level. However, reduction of the achieved maintenance level will lead to study discontinuation. The dosage of 50 mg as the daily intake during the study period, is decided based on clinical experience from private pain clinics from where medical cannabis is prescribed in Denmark (Clinic Horsted), and on dialogue with the pharmacists at Glostrup pharmacy, who will supply the investigational medicinal product and placebo. Glostrup pharmacy is experienced in producing cannabidiol pills for research purposes, and "cannabidiol" placebo pills that are identical in appearance, taste, and smell. Glostrup pharmacy will be responsible for the labelling of the cannabidiol and placebo tablet packages with a unique Dispensing Unit Number (DUN). The investigating site will ensure proper storage of the trial products, in a locked and secure temperaturecontrolled room. A non-blinded, non-investigator will ensure that participants are receiving the study drug or placebo according to the treatment allocation by parring DUN numbers and the recipient patient numbers in the e-CRF system. One investigator will be responsible for drug accountability. For each patient treated, the DUN number of the package will be documented, and the patients will be asked to return the empty packages after use for accountability. Proper destruction of unused drugs will be ensured.

8.5 Post-interventional observation period

After the termination of treatment, a post-interventional observational period of 12 weeks will be initiated. This period is essential for the assessment and monitoring of the effects of drug cessation on pain, sleep quality, pain self-efficacy, activities of daily Living, quality of life and the overall burden of fibromyalgia symptoms, as well as potential adverse events.

9. ENDPOINTS

Endpoints are selected based on the fibromyalgia core domains, identified by the OMERACT 9 (Outcome measures in Rheumatology) initiative [44].

9.1 Outcome measures

The following validated Patient Reported Outcomes (PRO's) are applied in this study:

AUTHOR: [name], The Parker Institute, Copenhagen University Hospital

DATE: 2020-12-14

Protocol number P142; Version: 4; EudraCT: 2019-002394-59, Regional Ethical Committee Journal Number H-20047715. ClinicalTrials.gov Identifier:

- The Fibromyalgia Impact Questionnaire Revised (FIQ-R) [45]
- The Pittsburgh Sleep Quality Index (PSQI) [46]
- The EuroQol Group Self-Rated Health Questionnaire (EQ5D) [47]
- The Activities of Daily Living Questionnaire ADL-Q [48]
- The Pain Self-Efficacy Questionnaire (PSEQ) [49,50]
- The Depression, Anxiety, Stress Scale (DASS-21)[51]
- The Perceived Stress Scale (PSS)[52]
- Columbia-Suicide Severity Rating Scale (C-SSRS) [53]
- The Simplified Nutritional Appetite Questionnaire (SNAQ) [54]
- The Fibromyalgia Sensory Hypersensitivity Scale (FSHSS) [Developed at the Parker Institute]

In addition, a basic information questionnaire will be applied at the screening visit to collect data on demography, medical and medication history.

Observation-based outcomes are also applied in the study. The Assessment of Motor and process skills (AMPS) [55], is an observation-based, standardized evaluation of the individual's ability to perform and complete activities of daily living. The AMPS motor ability measure reflects the level of effort, fatigability and clumsiness observed during performance of a task, whereas the AMPS process ability measure reflect how timely and well organized the tasks are performed [55]. Assessment of pressure pain threshold and tolerance is performed using computerized cuff pressure algometry [56]. Pain threshold is defined as the pressure of the cuff at the subjects first sensation of pain when applying constantly rising pressure. Pain tolerance is defined as the worst tolerable pain caused by the pressure stimulation and the pressure is switched off by the patient [56]. To assess muscle fatiguability, a static muscle exhaustion test is performed during which surface electromyography is recorded (non-invasively). From the surface electromyography signal, the degree of peripheral (muscular) and central (central nervous system) fatigue is quantified [7]. Hair clippings will be sampled from all participants and analyzed to assess cortisol contents as a biomarker for prolonged stress [57]. Objectively measured information on sleep and physical activity will be collected using the triaxial accelerometer device SENS MOTION® activity measurement system [58]. Body weight (±0.1 kg) will be measured using an electronic scale. To estimate body composition, bioimpedance measurement (BIA) will be conducted using the ImpediMed, model SFB7 [59], produced in Queensland, Australia, which measures impedance over a spectrum of frequencies. Waist and hip circumferences (WHR) will be measured using a tape measure to the nearest 0.1 cm, from which WHR will be calculated (waist circumference / hip circumference) are included as a measure of bodyfat distribution.

9.2 Primary endpoint

The primary endpoint is change in pain intensity from baseline to week 24, measured on a 0-10 Pain Numeric Rating scale (NRS) included in the FIQ-R. To facilitate interpretation of the pain intensity measure,

AUTHOR: [name], The Parker Institute, Copenhagen University Hospital

DATE: 2020-12-14

 $\textbf{Protocol number} \ \textbf{P142; Version:} \ \textbf{4; EudraCT:} \ \textbf{2019-002394-59, Regional Ethical Committee Journal Number} \ \textbf{H-20047715. ClinicalTrials.gov}$

Identifier:

the findings will also be communicated as the proportion of patients achieving more than 30% and 50% pain reduction on the FIQ-R Pain Numeric Rating scale.

9.3 Key secondary endpoints

- 1. Change in sleep quality: PSQI subjective sleep quality domain
- 2. Change in sleep duration: PSQI, sleep duration domain
- 3. Change in objectively measured sleep duration and patterns: accelerometer data
- 4. Change in activities of daily living: AMPS and ADL-Q total
- 5. Change in Quality of life: EQ5D total

9.4 Exploratory secondary endpoints

- 1. Change in sleep latency: PSQI, sleep latency domain
- 2. Change in pain self-efficacy: PSEQ total
- 3. Change in stiffness: FIQ-R stiffness subscale
- 4. Change in energy level: FIQ-R energy subscale
- 5. Change in objectively measured physical activity: accelerometer data
- 6. Change in feeling rested: FIQ-R rested subscale
- 7. Change in depression: FIQ-R depression subscale
- 8. Change in depression, anxiety and stress: DASS depression anxiety and stress scale
- 9. Change in anxiety level: FIQ-R anxiety subscale
- 10. Change in perceived stress: PSS perceived stress scale
- 11. Change in cortisol concentration in hair: hair clipping analysis
- 12. Change in memory problems: FIQ-R memory subscale
- 13. Change in tenderness level (tenderness to touch): FIQ-R tenderness subscale
- 14. Change in balance problems: FIQ balance subscale
- 15. Change in environmental sensitivity: FIQ environmental sensitivity subscale and FSHSS
- 16. Change in pressure pain threshold and tolerance: Cuff algometry
- 17. Change in muscle fatiguability
- 18. Change in appetite: SNAQ
- 19. Change in body weight
- 20. Change in body composition: BIA
- 21. Change in body fat distribution: WHR

AUTHOR: [name], The Parker Institute, Copenhagen University Hospital

DATE: 2020-12-14

 $\textbf{Protocol number} \ \textbf{P142; Version:} \ \textbf{4; EudraCT:} \ \textbf{2019-002394-59, Regional Ethical Committee Journal Number} \ \textbf{H-20047715. ClinicalTrials.gov}$

Identifier:

10. STUDY PROCEDURES

10.1 Visit description

Prescreening (week -8 to-4)

- Exchange of oral information and general eligibility screening; done by telephone by study nurse or secretary
- Written trial information material and information on trial subjects' rights is sent to potential participants

Screening visit (week -4 to 0)

- Information about the trial and participants' rights is repeated
- Signed informed consent is obtained by the study physician (primary investigator or sub investigator)
- Eligibility, inclusion and exclusion criteria are reviewed
- Physical examination to assess for eligibility and ensure safety
- Medical history
- Medication history
- Vital signs (blood pressure and pulse), body weight and height
- Electrocardiogram (ECG 12-lead)
- Blood testing for standard biochemistry and hematology (see section 8.1)
- Urine test (pregnancy, opioids, cannabinoid (TSH))
- Vital signs
- Body weight
- ECG
- Accelerometer data
- Adverse events

Randomization (week 0)

- Medical history
- Medication history
- PROMs
- AMPS
- Cuff Algometry

AUTHOR: [name], The Parker Institute, Copenhagen University Hospital

DATE: 2020-12-14

Protocol number P142; Version: 4; EudraCT: 2019-002394-59, Regional Ethical Committee Journal Number H-20047715. ClinicalTrials.gov Identifier:

- Muscle fatiguability
- Vital signs
- Body weight
- Body composition (BIA)
- Body fat distribution (WHR)
- Hair cortisol level
- Accelerometer data
- Adverse events
- Blinded allocation to cannabidiol 50 mg or placebo
- Medicine dispense

Drug intervention (week 0 to 24)

Up titration period (week 2) and telephone visits (weeks 1, 8 and 16)

- Adverse events
- Compliance assessment
- Accelerometer data
- Vital signs (week 2)

Follow-up visits (Week 4, 12 and 20)

- PROMs
- Vital signs
- Body weight
- Blood testing with standard biochemistry and hematology (week 12)
- Urine test (pregnancy, opioids, cannabinoid (TSH)) (week 12)
- Adverse events
- Compliance assessment
- Medicine handout

End of trial (week 24)

- Physical examination
- PROMs
- AMPS
- Hair cortisol level

AUTHOR: [name], The Parker Institute, Copenhagen University Hospital

DATE: 2020-12-14

Protocol number P142; Version: 4; EudraCT: 2019-002394-59, Regional Ethical Committee Journal Number H-20047715. ClinicalTrials.gov Identifier:

- Cuff algometry
- Muscle fatiguability
- Vital signs
- Blood testing with standard biochemistry and hematology
- Urine test (pregnancy, opioids, cannabinoid (TSH))
- Body weight
- Body composition (BIA)
- Body fat distribution (WHR)
- Accelerometer data (collection start one week prior to end of trial)
- Adverse events
- Compliance assessment

End of follow-up (week 36)

- PROMs
- Vital signs
- Body weight
- Adverse events

AUTHOR: [name], The Parker Institute, Copenhagen University Hospital

DATE: 2020-12-14

Protocol number P142; Version: 4; EudraCT: 2019-002394-59, Regional Ethical Committee Journal Number H-20047715. ClinicalTrials.gov Identifier:

10.2 Visit schedule

10.2 VISIT SCHEdule	1			I								
Study phases	Prescreening	Screening	Randomization			Drug	interve	ention			End of trial	End of follow-up
			U	p-titra	tion	Follow-up visits						
Week no.	-84	-4 - 0	0	1*	2	4	8*	12	16*	20	24	36
Information	х	Х	х									
Eligibility screening	х	х										
Informed consent		Х										
Physical examination		х									Х	
Medical history		х	Х									
Medication history		х	х									
Blood testing		х						х			Х	
Urine test		х						Х			Х	
PROMs			х			Х		х		х	Х	х
AMPS			х								Х	
Cuff algometry			Х								Х	
Muscle fatiguability			х								Х	
Vital signs (BP, pulse)		х	Х		х	Х		х		х	Х	х
Body weight		х	Х			Х		х		х	Х	х
Body composition			х								Х	
Body fat distribution			х								Х	
Height		Х										
ECG (12-lead)		х										
Hair clipping (Cortisol)			х								Х	
Accelerometer data		Х	х								Х	
Adverse events		Х	х	х	х	Х	Х	Х	х	х	Х	х
Medicine allocation			х									
Medicine dispense			х			Х		Х		х		
Compliance				х	х	Х	х	х	х	х	х	
assessment												

^{*} Visits to be performed via telephone call

Visit window is ± 7-days.

AUTHOR: [name], The Parker Institute, Copenhagen University Hospital

DATE: 2020-12-14

 $\textbf{Protocol number} \ \textbf{P142; Version:} \ \textbf{4; EudraCT:} \ \textbf{2019-002394-59, Regional Ethical Committee Journal Number} \ \textbf{H-20047715. ClinicalTrials.gov}$

Identifier:

11. SAFETY CONSIDERATIONS

11.1. Potential side effects, risks, and discomforts for study subjects

Common side effects (1-10%) of drugs containing both THC and CBD (Sativex), are overall feeling of weakness and uneasiness, reduced or increased appetite, diarrhea, nausea, dryness in the mouth, constipation, apathy, balance problems, depression, euphoria, feeling of intoxication, problems with memory and concentration, confusion, personality disorders, sleepiness, difficulty speaking, blurred vision. Rare side effects (0,1-1%) are abdominal pain, hypertension, hallucinations, psychosis, suicidal behavior and fainting. THC and CBD may interact with and enhance the effects of sedatives and alcohol [60]. According to the current legal practice in Denmark, it is not allowed to drive a car when using medical THC. CBD alone is shown to have a favorable safety profile compared to the CBD + THC combined or THC alone.

The most commonly reported side effects of CBD (seen in at least 10%), are tiredness/fatigue, problems sleeping, feeling weak, changes in appetite and weight, infections, diarrhea and rash [61]. More serious and rare side effects (seen in at least 1 %), are hypersensitivity reactions, hepatocellular injury and suicidal behavior and ideation [62]. However, these serious side effect have been reported in patients diagnosed with epilepsy who have been undergoing treatment with daily Cannabidiol dosages of 5 mg per kilogram body weight [62], which could be six times the dosages prescribed in the current CANNFIB study.

11.2 Adverse events

Potential adverse events (AE) will be assessed for at every visit throughout the study, and all evidence of a clinical and/or laboratory AE will be documented in the patient's medical file and recorded in the patient e-CRF. The primary investigator or sub investigator will assess the seriousness of the AE and the probability of the AE being related to the study drug. Subsequently the AE will be followed up on its duration and whether it is resolving or not to a satisfactory conclusion, and any concomitant medication taken in relation to the AE, will be recorded in the patient's medical file and. All adverse events will be documented from the start of the study drug administration to 12 weeks after the discontinuation of the study drug.

The Parker Institute as the investigator of the study, will be responsible for the reporting of all Serious Adverse Events (SAE), which is defined as an AE resulting in death, being life-threatening, requiring hospitalization or resulting in significant disability. If a SAE occur, the investigator will report it within 24 hours of the site being made aware of the SAE, to the sponsor. The Parker Institute will as the sponsor of the study, be responsible for the reporting of any deadly or life-threatening Suspected Unexpected Serious Adverse Reactions (SUSARS) that may occur, to the Danish Medicines Agency, as soon as possible and no later than 7 days after being made aware of the SUSAR. The Parker Institute will also be responsible for reporting any additional information regarding the SUSAR, within 8 days of the initial reporting. The Parker

AUTHOR: [name], The Parker Institute, Copenhagen University Hospital

DATE: 2020-12-14

Protocol number P142; Version: 4; EudraCT: 2019-002394-59, Regional Ethical Committee Journal Number H-20047715. ClinicalTrials.gov

Identifier:

Institute will be responsible to report any other SUSARs to the Danish Medicines Agency within 15 days after being made aware of the SUSAR.

The Reference document to be used to assess whether a reported SAE is suspected or unexpected, is the product resume of Epidyolex in which the active ingredient is Cannabidiol [63].

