Robustness is a concept that refers to the sensitivity of the overall conclusions to various limitations of the data, assumptions, and analytic approaches to data analysis. Robustness implies that the treatment effect and primary conclusion of the CANNFIB trial is not substantially affected when analyses are carried out, based on alternative assumption or analytic approaches (11).

Harms

Data on adverse events (AE) are collected at all visits up to 36 weeks from baseline. The participants are interviewed about any adverse events occurring during the trial. We will provide information about the severity of the adverse event, and the action taken with regards to the AE i.e., whether any concomitant medication was taken, dose reduction or whether the study drug was paused, discontinued or if other actions was taken. The study physicians assess whether the AE is expected and possible relation to the study drug, based on the Summary of Product Characterizing for CBD as a reference document. The Common Terminology Criteria for Adverse Events (CTCAE version 5.0 will be used as the reference document for graduation the severity of the AE and whether the AE is a Serious Adverse Event (SAE). Harms observed in 5% or more in the study population are reported in this study. Based on the ITT population, the following safety data will be summarized in the final analysis report:

- All adverse events are summarized with a breakdown of severity categories (mild, moderate, severe, and serious), for both treatment arms
- The number and percentages of participants who withdraw from the intervention because of adverse events are reported for both treatment arms.

Statistical software

All analyses will be performed using the statistical software SAS version 9.4 (SAS Institute, Cary, NC, USA).

Figures and Tables Outline

Figure 1. Trial Profile: Patient Flow Throughout the Final Trial

Table 1. Baseline Characteristics for the Intention-To-Treat Population

Table 2. Primary and Key Secondary outcomes at 24 weeks from Baseline in the ITT Population

Figure 2a. The average trajectory in each group for the Pain Intensity (Average pain during the last 7 days) over time from baseline (week 0) to endpoint (week 24) and follow-up (week 36)

Figure 2b. Scatterplot of the individual values of after vs baseline in pain intensity in the intervention group and placebo group from before (at baseline) and after the intervention (at week 24).

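### The protocol's four-criterion SAE definition has no place for medically important events or birth defects, the SAP uses a different reference for seriousness, and reported pregnancies are not followed to outcome

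*Combined protocol and SAP*

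**What the plan says.** **Definition.** Protocol 11.2 defines an SAE as one "defined as an AE resulting in death, being life-threatening, requiring hospitalization or resulting in significant disability". The wording is a definition, not a list of examples. "The primary investigator or sub investigator will assess the seriousness of the AE", but no criterion lets that physician call an event serious on medical grounds alone.

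**What the definition triggers.** For an SAE, "the investigator will report it within 24 hours of the site being made aware of the SAE, to the sponsor". The SUSAR reports to the Danish Medicines Agency (7 days if fatal or life-threatening, otherwise 15) also presuppose seriousness.

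**Risks named.** Section 11.1 states: "More serious and rare side effects (seen in at least 1 %), are hypersensitivity reactions, hepatocellular injury and suicidal behavior and ideation".

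**Collection.** "All adverse events will be documented from the start of the study drug administration to 12 weeks after the discontinuation of the study drug".

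**Pregnancy.** Section 7.4 states: "In the event of subjects becoming pregnant during the trial, they are instructed to notify the investigator immediately". For male participants: "If a partner of a male participant becomes pregnant, the investigator should be notified immediately". Neither sentence is followed by a report to the sponsor or by collection of the outcome.

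**SAP.** Under Harms, CTCAE v5.0 "will be used as the reference document for graduation the severity of the AE and whether the AE is a Serious Adverse Event (SAE". The same section lists serious as a fourth category after mild, moderate and severe, and limits reporting of individual harms to those seen in at least 5% of the study population.

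**The concern.** The trial looks for two of its three named risks in outpatients. Liver tests are scheduled at weeks 12 and 24 after the screening sample, and the C-SSRS is among the questionnaires at weeks 0, 4, 12, 20, 24 and 36. A raised liver enzyme on a routine sample, or new suicidal ideation handled without hospitalisation, is a plausible result of such testing and may meet none of the four criteria. Applied as written, 11.2 makes it non-serious, although 11.1 uses the word serious for that kind of event.

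Safety is a stated aim of the trial. The SAE row of Table 3 is the main place where a rare but important harm would be visible by arm. If the two documents define that row differently, a reader cannot tell what it counts. For pregnancy, a birth defect falls outside the definition, and in most cases outside the collection period as well.

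**Working it through.** **1. Passages side by side.**

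| Question | Protocol 7.4, 11.1, 11.2 | SAP, Harms and Table 3 |
|---|---|---|
| What makes an AE serious? | Four outcomes only | CTCAE v5.0 |
| Medically important by judgement? | Not listed | Not stated |
| Birth defect? | Not listed | Not stated |
| Risks described as serious | Liver-cell injury, suicidal thoughts or behaviour, hypersensitivity | No liver or suicidality row in the Table 3 template |
| Pregnancy notified to | Investigator | Not mentioned |
| Pregnancy outcome collected? | Not stated | Not mentioned |

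No other section of either document adds a criterion.

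**2. A case traced through the rules.** Take a liver abnormality on the week-12 sample in a patient who is not hospitalised, not in danger and not disabled. Under 11.2 it is an AE, recorded and followed until resolved. It is not an SAE, so the 24-hour report does not start and no SUSAR assessment is due. Under the SAP its status depends on how CTCAE v5.0 is read, which the SAP does not explain.

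**3. Visibility in Table 3.** The threshold for a named row is 5% of the ITT population: 0.05 × 200 = 10 patients. A non-SAE event in fewer than 10 patients appears only within the total, severity and, where relevant, withdrawal counts.

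**4. How many such events (illustrative).** Section 11.1 gives at least 1%. With about 100 patients on CBD, the expected number is 100 × 0.01 = 1.0, and the chance of at least one is 1 − (1 − p)^100:

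| Assumed rate p | Expected events | Chance of at least one |
|---|---|---|
| 0.5% | 0.5 | 39% |
| 1% | 1.0 | 63% |
| 2% | 2.0 | 87% |

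These are all occurrences. The documents do not say what share would meet none of the four criteria, so each expected count is an upper limit on misclassified events at that rate.

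**5. Pregnancy timing.** Assumption: about 38 weeks from conception to term. AE documentation for a completer ends at week 24 + 12 = 36.
- Conception at week 0: 0 + 38 = week 38, which is 2 weeks after the end.
- Conception at week 24: 24 + 38 = week 62, which is 26 weeks after the end.

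Every term birth from a conception during treatment therefore falls after collection stops. This shows timing only; the documents give no basis for how often a pregnancy would occur.

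**The case against.** **Events are not lost.** This stands. Section 11.2 records and follows all clinical and laboratory AEs. What is missing is SAE status and what it triggers.

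**The 24-hour report is largely internal.** This stands too. Section 16 says sponsor and site are the same, so a reader who infers that the sponsor would be left unaware goes beyond the text.

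**The named risks may never be SUSARs.** Expectedness is judged against the Epidyolex product summary, and 11.1 takes these risks from prescribing information for the same product. They may well be expected, but that summary is not in the documents. The SUSAR gap is therefore claimed only for medically important events that the reference does not list.

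**Too-low SAE counts do not follow.** A reader might conclude that Table 3 will understate SAEs. Because the SAP points to CTCAE and not to 11.2, the direction is not settled; what can be said is that the content of the row is unclear.

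**Prolonged hospitalisation is arguably covered.** An event that keeps a patient in hospital can be said to require hospitalisation. This needs clarification only.

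**Serious in 11.1 may be everyday usage.** Possibly. The two sections still need reconciling, because 11.2 leaves the physician no route to call such an event serious.

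**The 1% does not transfer directly.** Section 11.1 says these events were seen in epilepsy patients at doses that could be six times those used here, and 7.2 excludes impaired liver function, major depressive disorder and past suicidal behaviour.

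**Pregnancy is guarded against.** A negative test and contraception are required, and urine pregnancy tests recur at weeks 12 and 24. That lowers the likelihood but does not say what happens to a pregnancy once reported.

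**Conclusion.** The concern holds in a limited form. In the Version 4 text the seriousness definition is closed, omits medically important events and birth defects, does not match the protocol's own description of CBD risks, and differs from the SAP's reference. Pregnancy reporting stops at the investigator, with no outcome follow-up.

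The size is modest: on the protocol's own rate, about one event of the named kind among 100 CBD patients, for illustration only and before asking how many would meet a listed criterion. The pregnancy gap is 2 to 26 weeks past the end of collection for conceptions in weeks 0 to 24, given 38 weeks to term. The efficacy analyses are unaffected.

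Two further readings are tempting but unsupported. An event does not need hospitalisation to count, since a life-threatening or disabling event qualifies without it. Nor does all harm to an exposed pregnancy escape: harm to a participant that is fatal, life-threatening or requires hospitalisation is already an SAE. The gap is birth defects, lesser harm, partner pregnancies and onward reporting.

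The conclusion rests on Version 4, dated 2020-12-14. The SAP cites Version 5 of 17.08.2023, which may already have corrected this and should be checked first.

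**What to change.** 1. Reconcile protocol 7.4, 11.1 and 11.2 with the SAP's Harms section into one definition of seriousness. Keep the four criteria and add (a) congenital anomaly or birth defect, and (b) any event the study physician judges medically important, stated to cover the risks that 11.1 calls serious. Clarify that prolongation of a hospital stay counts. Use CTCAE for severity grading only.
2. State in 7.4 that a pregnancy in a participant or partner is reported to the sponsor, and that its outcome is collected by telephone even after week 36.
3. Use this definition for Table 3's SAE row. Since AEs are already in the e-CRF, reclassify them blinded to allocation before the analysis, and record in the SAP that this was done.

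**Cost.** Wording in two documents, a slightly higher SAE count and rare late telephone contacts. By the SAP's date of 03.01.2024 all 200 patients had been randomised and last visits were expected in February 2024, so much of the work is retrospective review of recorded AEs and contact about any pregnancy already notified. The 24-hour report cannot be recovered for past events.
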